### 9.3 Selection of clinical trial population

Approximately 40 subjects will be included in this clinical trial.

- E6011 group 20 subjects: Placebo group 20 subjects
- · 22 Japanese subjects: 18 Non-Japanese subjects (rough estimate)

· 8 biologic-naive patients (rough estimate)

Subjects that meet all the following inclusion criteria and do not fall under any of the exclusion criteria shall receive the IMP.

#### 9.3.1 Inclusion criteria

Subjects who meet all the following criteria are eligible to participate in this clinical trial.

- (1) Crohn's disease patients aged 18 or over and under 65 on the date of consent.
- (2) Patients diagnosed on basis of clinical findings, endoscopic findings, etc. with small intestine-type, small and large-intestine type, or large-intestine type Crohn's disease at least 12 weeks before giving consent.
- (3) Patients with a baseline (at Week 0 before the start of IMP administration) disease severity ranging from moderate to severe. CDAI score between 220 and 450, and a PRO2 score between 14 and 34.
- (4) Patients with a Simple Endoscopic Score for Crohn's Disease (SES-CD) ≥7 (or for patients with isolated ileal disease, ≥4 in ileum segment) in the screening period, with one or more ulcers (in SES-CD score, ulcer presence subscore ≥ 1 in any segment) assessed by colonoscopy and confirmed by a centralised review.
- (5) Patients who received adrenocorticosteroids or immunomodulators in the past, but showed no therapeutic response (insufficient response) or the drugs were not tolerated (intolerance). Alternatively, patients who cannot taper adrenocorticosteroids (dependence). Alternatively, patients who showed no therapeutic response after administering biologic(s) (primary nonresponse), patients who initially showed therapeutic response but it lessened or disappeared afterwards (secondary nonresponse), or patients who did not tolerate the drug (intolerance). (Detailed criteria are described in Attachment 7 and Attachment 8).
- (6) If the patients are taking 1,200 kcal/day or less enteral nutrition, the dosage and administration have not changed for at least 4 weeks prior to the start of the IMP administration.
- (7) If the patients are taking aminosalicylic acid (5-ASA), salazosulfapyridine, or antibiotics for the treatment of Crohn's disease (metronidazole, ciprofloxacin, etc.), the dosage and administration have not changed for at least 4 weeks prior to the start of the IMP administration.
- (8) If the patients are taking under 30 mg/day of oral prednisolone (or equivalent adrenocorticosteroid) or 9 mg/day or less of oral budesonide, the dosage and administration have not changed for at least 4 weeks prior to the start of the IMP administration.
- (9) If the patients are taking azathioprine (AZP), 6-mercaptopurine (6-MP) or methotrexate (MTX), the dosage and administration have not changed for at least 8 weeks prior to the start of the IMP administration.
- (10) Patients who have received a sufficient explanation about the compliance rules of this clinical trial, who are willing to comply with them, and who are able to do so.
- (11) Patients who voluntarily gave a written consent to participate in this clinical trial.

#### 9.3.2 Exclusion criteria:

Patients who meet any of the following criteria shall be excluded from this clinical trial.

(1) Patients diagnosed with ulcerative colitis or indeterminate colitis (refers to cases in which there is a difficulty distinguishing between Crohn's disease and ulcerative colitis, intermediate colitis).

- (2) Patients diagnosed with gastrointestinal epithelial dysplasia.
- (3) Patients who have an abscess or are suspected to have one (however, patients with perianal abscess whose symptoms are stable with treatment, such as drug treatment or drainage, are not excluded).
- (4) Patients with an artificial anus, ileo-anal pouch or fistula (however, patients with anal fistula whose symptoms are stable with treatment, such as drug treatment or drainage, are not excluded).
- (5) Patients with symptomatic or high-grade gastrointestinal stenosis (patients who require expansion by endoscopy or who require have SES-CD score stenosis sub-score of 3, etc.).
- (6) Patients who, after undergoing small bowel resection, have been diagnosed with a short bowel syndrome, which makes maintaining caloric intake difficult.
- (7) Patients who have newly started seton drainage treatment within 12 weeks prior to the start of the IMP administration.
- (8) Patients who have undergone bowel resection or a gastrointestinal surgery within 24 weeks prior to the start of the IMP administration.
- (9) Patients who tested positive for *C. difficile* toxin test in the screening period.
- (10) Patients who tested positive for HIV, hepatitis B surface antigen (HBsAg), hepatitis B surface antibody (anti-HBs), hepatitis B core antibody (anti-HBc), hepatitis B virus DNA (HBV-DNA), hepatitis C virus antibody (anti-HCV), or human T cell leukemia virus type 1 antibody (anti-HTLV-1) in the screening period (however, this excludes patients who tested positive only for anti-HBs, clearly shown to be due to hepatitis B vaccination). Patients who tested negative for HBsAg and quantitative HBV-DNA and positive for anti-HBc antibody and/or anti-HBs antibody may participate in the clinical trial as long as the Principal Investigator or Sub-investigator takes proper measures such as monitoring HBV-DNA based on (not restricted to the following)
  - For Japan: Guidelines for measures against hepatitis B arising due to immunosuppression or chemotherapy
  - For Poland: Recommendations for the treatment of chronic viral hepatitis B in 2018 by Polish Group of Experts for HBV
  - For Hungary: Diagnosis and treatment of chronic hepatitis B and D. Hungarian national consensus guideline
  - For Czech Republic: EASL (European Association for the Study of the Liver) 2017 Clinical Practice Guidelines on the management of hepatitis B virus infection
  - For Russian Federation: Order of Ministry of Health of Russian Federation #786H "On approval of the standard of specialized medical care for chronic viral hepatitis B" dd. 09.11.2012

In addition, patients who tested positive for HCV antibody and who were at least 24 weeks post-treatment may participate in the clinital trial as long as negative HCV-RNA is confirmed during the screening period.

(11) Patients with positive or repeated indeterminate (inconclusive) results on the TB test (QuantiFERON ® -TB Gold test or T-SPOT ® TB test). However, patients with indeterminate (inconclusive) results on repeated tests may be included in this clinical trial if they are started on prophylactic isoniazid least 21 days prior to the start of IMP administration. (The dose is generally 300 mg/day. If the patient has a low body weight, the dose is to be 5 mg/kg a day. The drug is administered for approximately 9 months.) Prophylactic treatment should be given in accordance with the local guidelines.

- (12) Patients with findings showing a history of tuberculosis on a chest X-ray test in the screening period.
- (13) Patients with findings of neurological symptoms such as motor impairment, cognitive disorder, language disorder or dysphagia in the evaluations during the screening period.
- (14) Patients with a WBC count of less than 3,000/μL or blood CD4+ cell count under 200/μL in the screening period tests.
- (15) Patients with a medical history of clinically significant vasculitis.
- (16) Acute myocardial infarction, unstable angina pectoris, cerebral infarction, and symptomatic cerebral haemorrhage patients.
- (17) Patients whose AST or ALT was more than three times the upper normal limit in the screening period tests or patients whose serum creatinine level was more than 1.5 times the upper normal limit in the screening period tests.
- (18) Patients with a QTcF exceeding 450 ms repeatedly in standard 12-lead ECG tests in the screening period tests.
- (19) Patients who have undergone cytoapheresis (granulocytapheresis; GCAP) within 2 weeks prior to the start of the IMP administration.
- (20) Patients who required any one of the following treatments of infection; "hospitalization within 4 weeks prior to the start of IMP administration", "intravenous treatment of antibiotics (including antiviral drugs) within 4 weeks prior to the start of IMP administration", or "oral treatment of antibiotics (including antiviral drugs) within 2 weeks prior to the start of IMP administration".
  - Furthermore, with regard to the novel coronavirus infection (COVID-19), patients who required any one of the following treatments; "hospitalization within 4 weeks prior to the start of IMP administration", "any intravenous treatment within 4 weeks prior to the start of IMP administration" or "any oral treatment within 2 weeks prior to the start of IMP administration".
- (21) Patients who received total parenteral nutrition (TPN), peripheral parenteral nutrition (PPN), or enteral nutrition exceeding 1200 kcal/day within 4 weeks prior to the start of the IMP administration.
- (22) Patients who received ≥30 mg/day of oral prednisolone (or an equivalent adrenocorticosteroid), adrenocorticosteroid injection, enema or suppository within 4 weeks prior to the start of the IMP administration.
- (23) Patients who received cyclosporine, mycophenolate mofetil, or tacrolimus within 8 weeks prior to the start of the IMP administration (excluding topical use).
- (24) Patients who received adalimumab, infliximab, certolizumab pegol, vedolizumab or ustekinumab

- (including biosimilars) within 8 weeks prior to the start of the IMP administration.
- (25) Patients vaccinated with live vaccines within 12 weeks prior to the start of the IMP administration or patients who received a vaccine that is considered to have a risk of infection, such as a virus vector vaccine that uses a virus that retains its ability to proliferate within 12 weeks prior to the start of the IMP administration
- (26) Patients who received an immunoglobulin preparation or a blood product within 24 weeks prior to the start of the IMP administration.
- (27) Patients who have received natalizumab or E6011 in the past.
- (28) Patients with a history of a malignant tumour, lymphoma, leukemia, or lymphoproliferative disorders, or with complications thereof. However, this does not include completely resected skin cancers (epithelial cell cancers or basal cell cancers) and cervical cancers with no metastasis or recurrence observed for 5 more years at the time of giving consent.
- (29) Patients with immunodeficiency or a history of HIV infection.
- (30) Patients with a history of severe allergy (shock, anaphylaxis-like symptoms).
- (31) Patients currently taking part in another clinical trial (including the post-observation period), or patients who were participating in another trial using an IMP or investigational medical device within 28 days (or within five times the length of the half-life period of the IMP, whichever is longer) prior to giving consent.
- (32) Patients who received a faecal microbiota transplant (FMT), mesenchymal stem cell, etc. within 24 weeks prior to giving consent.
- (33) Female patients of childbearing potential who had a positive result on the pregnancy test at screening or baseline, as well as lactating patients.
- (34) Female patients of childbearing potential who:
  - have not been on a highly effective method of contraception within 28 days prior to the start of IMP administration. The following are highly effective contraception methods:
  - Sexual abstinence (if preferred by subjects as their regular lifestyle)
  - Use of intrauterine device (IUD)
  - Contraceptive implant
  - Use of oral contraceptives
  - (The same oral contraceptive is to be used at a set dose for more than 28 days prior to the start of the IMP administration, and continued throughout the clinical trial and for 70 days after the last administration of the IMP)
  - The male partner has undergone vasectomy and azoospermia has been confirmed.
  - Patients who do not agree to continue using one of the highly effective contraception methods described above throughout the clinical trial and for 70 days after the last administration of the IMP
  - If the use of the aforementioned contraception methods is not appropriate or not allowed, the patients are required to consent to use another medically appropriate contraception method, i.e. a double-barrier method (combined use of a condom and contraceptive diaphragm, or a

- spermicide-containing cervical/vault cap, etc.)
- All females are deemed to have childbearing potential. However, postmenopausal women (menopausal age patients who have not menstruated for at least 12 consecutive months, which has been confirmed not to be due to other factors, or is not suspected to be due to other factors) and women who have undergone surgical sterilization (patients who have undergone bilateral tubal ligation, hysterectomy, or bilateral oophorectomy more than one month prior to the IMP administration) are excluded from this rule.
- (35) Potential male patients with female partners of childbearing potential:
  - that have not undergone proper vasectomy (azoospermia can not be confirmed) who (or whose partners) do not agree to use contraception employing one of the methods listed in the exclusion criteria (34) during the clinical trial and for 70 days after the last administration of the IMP (however, if the female partner does is not of childbearing potential, the subject can participate in the trial)
  - patients whose female partner is pregnant and do not agree to use latex or synthetic condoms during the clinical trial and for 70 days after the last administration of the IMP
  - The patients must not donate sperm during the clinical trial and for 70 days after the last administration of the IMP
- (36) Patients who were judged to be unsuitable for participation in this clinical trial by the Principal Investigator or Sub-investigator.

#### 9.3.3 Termination of subject treatment or evaluation

The Principal Investigator or Sub-investigator may terminate the subjects' participation in the clinical trial at any time for safety reasons or reasons related to the conduct of the clinical trial. The subjects themselves may request discontinuation of the IMP administration or participation in the clinical trial at any time without providing explanation.

All subjects who discontinue the clinical trial after the start of the IMP administration are to undergo assessments at discontinuation outlined in the study schedule (Table 4) (see "9.5.5" Subject completion and withdrawal").

Note that if any of the following applies to the subject, he or she is to be discontinued.

- (1) The subject has experienced adverse events which make continuation difficult.
- (2) The subject's pregnancy has been confirmed.
- (3) The subject has been deemed to be ineligible to participate in the clinical trial.
- (4) It has become difficult for the subject to continue to use a concomitant drug/concomitant therapy as instructed.
- (5) The subject requires a surgical operation.
- (6) The subject has been diagnosed with gastrointestinal epithelial dysplasia.
- (7) The subject has been diagnosed with a malignant tumour.
- (8) The subject has less than 70 reduction in the CDAI at Week 24 (rescue period) compared to baseline and Week 12.

#### 9.4 Treatment method

#### 9.4.1 IMP administration method

The dose of E6011 corresponding to the subject's weight is to be diluted with a physiological saline solution to prepare a 10 mg/kg E6011 dosing solution (approximately 100 mL). The physiological saline solution used to dilute E6011 is to be used as a placebo. The weight measurements used in the weight-dosage conversion to establish dosage (full dose) are to be the measurements taken on Week 0, Week 12, Week 24, Week 36 and Week 48 (only subjects moving on the rescue period), and the conversion dosage (full dose) may not change even if the patient gains or loses weight in between the measurements. IMP preparation procedure details are listed in Attachment 4.

The IMP is to be infused intravenously through an in-line filter (pore size:  $0.2 \mu m$ ) using an infusion pump over approximately 30 minutes (including saline flush). If drug hypersensitivity thought to be related to the IMP administration is observed, the subsequent infusion rate can be reduced, and the patient may be prophylactically premedicated with antihistamines and antipyretics.

The IMP is to be administered after all investigations scheduled for that day, excluding post-administration blood collection for the purpose of measuring serum E6011 concentration, have been completed.

The subject is to stay in the hospital for 60 minutes after the first and second administration in the remission-induction period and the rescue period, and is allowed to leave after safety has been confirmed.

The IMP is to be administered in the following periods (Table 1).

- Remission-induction period: E6011 or placebo is to be administered with repeat IV dosing to the E6011 10 mg/kg group or placebo group in Week 0, Week 1, Week 2, and every 2 subsequent weeks until Week 10.
- Rescue period: 10 mg/kg of E6011 is to be administered with repeat IV dosing in Week 12, Week 13, Week 14, and every 2 subsequent weeks until Week 22.
- Extension period: 10 mg/kg of E6011 is to be administered with repeat IV dosing every 4 weeks from Week 12 to Week 48 to remission-induction period responders, and from Week 24 to Week 60 after the completion of the rescue period to remission-induction period non-responders.

Table 1 IMP administration method

IMP	Dosage	Dosage form	Administration method	Administration period
E6011	10 mg/kg	Aqueous solution	10 mg/kg of E6011 dosing solution (approximately 100 mL) is to be infused intravenously over the period of approximately 30 minutes.	Remission-induction period: 12 weeks Rescue period: 12 weeks Extension period: 40 weeks
Placebo	N/A	Aqueous solution	The physiological saline solution (approximately 100 mL) is to be infused intravenously over the period of approximately 30	Remission-induction period: 12 weeks Rescue period: No administration

Date: 18-Apr-2022 version 11.0 Confidential Page 34 of 80

!	minutes.	Extension period: No
		administration

N/A: Not applicable

The Principal Investigator shall appoint the Clinical Trial Centre's pharmacist or a person with appropriate qualifications as the unblinded trial staff (unblinded trial pharmacist, unblinded trial doctor, or unblinded trial coordinator). Until maintaining the blinding is no longer necessary, such as at code break, only the unblinded trial pharmacist or unblinded trial doctor can prepare the IMP. The unblinded trial pharmacist or unblinded trial doctor, upon confirming the subject's allocation group and the subject's weight, is to prepare an E6011 dosing solution. The unblinded trial pharmacist or unblinded trial doctor is to create an IMP preparation record and deliver prepared IMP to the IMP administration trial staff, maintaining the blinding. Only an IMP administration trial staff who has undergone a proper training can administer the IMP. In the double-blind period, the unblinded trial pharmacist or unblinded trial doctor is to dispense the IMP after placing a semi-transparent or non-transparent concealing cover on the intravenous drip bottle sealed using a sticker, and after the IMP administration has been completed, the unblinded trial staff is to confirm that the seal sticker is still intact indicating that the concealing cover has not been taken off from the bottle until the end of administration, and that the blinding is thus maintained.

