### 8.3 Exploratory objective

#### 9. Clinical trial plan

### 9.1 General clinical trial design and plan

This is a multinational, multicentre, randomised, double-blind, placebo-controlled, parallel-group, early phase 2 clinical trial. This clinical trial consists of a screening period, remission-induction period (double blind), rescue period (open-label), extension period (open-label), post-observation period and follow-up period. Administration of the IMP is to start after confirming eligibility at baseline (at week 0 before the start of the IMP administration) upon having carried out the screening test within 42 days prior to the start of the IMP administration after obtaining consent.

Patients with moderate to severe active Crohn's disease are to be randomly allocated to an E6011 10mg/kg group and a placebo group (1:1) using stratified allocation in which race (Japanese/non-Japanese) and history of previous use of biologics (yes/no) are used as allocation factors. The administration volume (about 100 mL) is to be prepared based on the weight of the subject by diluting E6011 with a physiological saline solution, and infused intravenously over approximately 30 minutes. The physiological saline solution used to dilute E6011 is to be used as a placebo. The remission-induction period is to last 12 weeks, with E6011 or placebo administered in a double-blind method on Week 0, Week 1, Week 2, and once every two subsequent weeks up to Week 10, and the efficacy of E6011 is to be evaluated in Week 12. Subjects with a reduction in the CDAI (Crohn's Disease Activity Index) of 70 or more (responders) compared to baseline at evaluation on Week 12 are to move on to the open-label extension period. The extension period is to last 40 weeks, with 10 mg/kg of E6011 administered every four weeks from Week 12 to Week 48 and E6011 efficacy is to be evaluated at Week 52.

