Subjects with less than 70 reduction in the CDAI (non-responders) at evaluation in Week 12 are to move on to the rescue period. The rescue period is to last 12 weeks, with additional administrations of 10 mg/kg of E6011 in Week 12, Week 13, Week 14 and every two subsequent weeks up to Week 22. Subjects with a reduction in the CDAI of 70 or more compared to baseline/Week 12 at evaluation in Week 24 of the rescue period are to move on to the open-label extension period. The extension period is to last 40 weeks, with 10 mg/kg of E6011 administered every four weeks from Week 24 to Week 60 and E6011 efficacy is to be evaluated at Week 64. Patients with less than 70 reduction in the CDAI compared to baseline and Week 12 at evaluation in Week 24 are to be discontinued.

[figure not shown]
The Principal Investigator or Sub-investigator is to confirm that the subjects' data as of Week 12 of the remission-induction period (double-blind) has been completely entered into the eCRF by the time the first evaluation in the rescue period or extension period takes place. Blinding in the double-blind period is to be maintained until a database in the double-blind study period is locked.

The post-observation period consists of an assessment in person 28 days after the completion or discontinuation of the extension period of the clinical trial, and an assessment in person or over the phone 70 days after the last administration of the IMP. The follow-up period entails contacting the patients over the phone, etc. every 6 months until 2 years have passed from the last administration of the IMP to inquire whether they have experienced progressive multifocal leukoencephalopathy (PML).

Date: 18-Apr-2022 version 11.0 Confidential Page 25 of 80

Figure 1 shows the design of the clinical trial.

Figure 1 Clinical trial design

Responders at CDAI evaluation on Week 12 of the remission-induction period are to move on to the extension period, in which E6011 is administered every four weeks. Non-responders are to move on to the rescue period, and if the CDAI has improved by Week 24, they are to move on to the extension period, in which E6011 administered every four weeks. Subjects whose CDAI has not improved by Week 24 are to be discontinued.

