#### 9.1.4 Extension period

Subjects who finished evaluation at Week 12 of the remission-induction period and had a CDAI response of 70 or more, and subjects who moved on to the rescue period and finished evaluation at Week 24 with a CDAI response of 70 or more are to move on to their respective extension period. The extension period is to last 40 weeks, with 10 mg/kg E6011 administered in an unblinded manner every four weeks up to Week 48 or Week 60.

The Principal Investigator or Sub-investigator is to confirm before the first evaluation in the extension period is carried out that responders' data up to Week 12 of the remission-induction period (double-blind period) has been entered in the case report form. Blinding of each subject's treatment group is to be maintained until the database of the remission-induction period is locked.

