#### 9.4.4 Dosage selection in the clinical trial

In the 12-week period administration in Study 101, adverse events have been observed in 18 out of 28 subjects (64.3%). Of out these, adverse events observed in 2 or more subjects included nasopharingitis in 5 subjects (17.9%), and headache, nausea, anal abscess, and Crohn's disease in 2 subjects each (7.1%). Increase of E6011 dose-dependent incidence of side-effects and any concerning events were not observed,

Date: 18-Apr-2022 version 11.0 Confidential Page 36 of 80

and there were no safety or tolerability issues for Crohn's disease patients with the dosage range up to 15 mg/kg of IV E6011 administered biweekly. Concerning efficacy, although Study 101 is an open-label trial designed not to include a placebo group, evaluations up to Week 12 showed a trend towards improvement of clinical symptoms of Crohn's disease in each group (E6011 2 mg/kg group, 5 mg/kg group, 10 mg/kg group and 15 mg/kg group). Highest numbers of patients with improvement and patients who achieved remission were in the 10 mg/kg group.

By means of PK/PD analysis which used serum E6011 concentration and serum total FKN (the sum of free FKN and E6011-FKN complex) concentration in Study 001 and Study 002, a simulation of connectivity between E6011 used in Study 101 and its target, membrane-bound FKN, has been performed. Analysis showed that E6011 occupancy on membrane-bound FKN was approximately 99% with 10 mg/kg.

The above results showing that sufficient target occupancy and clinical symptom improvement can be expected with 10 mg/kg, it has been judged that in this clinical trial, which is a pivotal POC study, 10 mg/kg is the appropriate dosage to evaluate the efficacy of E6011 remission-induction. As in Study 101, dosing was set to take place in Week 0, Week 1, Week 2, and every 2 subsequent weeks.

As for the dosage and administration in the extension period, considering the fact that the subjects are patients who had experienced an improvement of their symptoms, as well as for subject convenience, 10 mg/kg, a dosage identical to the one used in the remission-induction period, was chosen to be administered intermittently at 4 week intervals.

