Pregnancy test f	0	0							0	0
C. difficile toxin test	0									
CDAI, PRO2		00		0	0		0		0	0
Haematology test, blood	0	0	0	0	0	0	0	0	0	0
biochemistry test, urinalysis										
Adverse event	←				l	ı	1	ı		 
Serum E6011 concentration g,		0	0	0	0	0	0	0	0	0
Serum anti-E6011 antibodies		0		0	0		0		0	0
Serum total FKN concentration h		0	0	0	0	0	0	0	0	0
Blood CD16 + monocytes, etc. (FCM) h		0	0	0	0				0	0
Blood CD16 + monocyte, etc. genetic markers h		0	0	0	0				0	0
Faecal calprotectin		0		0	0		0		0	0

- a. A written consent of the subject is required prior to undergoing tests and medication washout as part of the requirements to participate in this clinical trial.
- **b.** Endoscopic evaluations are performed by a centralised review.
- The IMP is to be administered after completing all assessments scheduled for that day (excluding serum E6011 concentration immediately after the end of administration).
- d. Height is measured during the screening period (on Visit 1) only.
  e. If abnormal neurological symptoms are found after IMP administration, the patient must be examined by a neurologist and undergo brain MRI (T1-weighted, FLAIR and diffusion-weighted imaging) within two weeks.
- Pregnancy test is conducted only in female subjects of childbearing potential.
- Blood samples are collected before and immediately after (within 10 minutes of) IMP administration between Week 0 and Week 10.

**h.** Test results are to be retained by the testing laboratories and not to be shared with Principal Investigators, Sub-investigators and trial coordinators until code break. Blood CD16+ monocytes, etc. (FCM) is only conducted in Japanese subjects

- i. Randomisation is to be performed at baseline (before the start of IMP administration in Week 0).
- j. As many specified tests and evaluations as possible should be conducted for the assessment at discontinuation.
- **k.** E6011 to be administered after the transition to the rescue period or Extension period.
- I. PML onset is to be investigated over the phone, etc. at six months, one year, one and a half years, and two years after the final IMP dose.
- m. E6011 not to be administered when discontinuing at Week 24 for a lack of CDAI response.
- n. To be conducted during the Week 24 visit or 28 days after discontinuation only when discontinuing at Week 24 for a lack of CDAI response.

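### The 60-minute post-infusion stay skips the extension period, so placebo subjects who respond at Week 12 receive their first two E6011 infusions with no stay required

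*Protocol*

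**What the plan says.** Section 9.4.1 of the protocol asks subjects to "stay in the hospital for 60 minutes after the first and second administration in the remission-induction period and the rescue period" and lets them leave once safety is confirmed. The extension period is not mentioned.

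Section 9.1 sends Week 12 responders of either arm (CDAI reduction of 70 or more) into the extension, "with 10 mg/kg of E6011 administered every four weeks from Week 12 to Week 48"; section 9.1.4 repeats this as "10 mg/kg E6011 administered in an unblinded manner every four weeks up to Week 48 or Week 60". Footnote k of Table 4 settles which period the Week 12 infusion belongs to: "E6011 to be administered after the transition to the rescue period or Extension period". The remission-induction rule therefore does not reach it.

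The original allocation stays hidden throughout: "Blinding in the double-blind period is to be maintained until a database in the double-blind study period is locked". Section 9.4.6 says the same for the open-label periods.

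Other protections do continue in the extension. Section 9.4.1 keeps the pump infusion of about 30 minutes, provides that "If drug hypersensitivity thought to be related to the IMP administration is observed, the subsequent infusion rate can be reduced" and allows premedication in that event, and states that "Only an IMP administration trial staff who has undergone a proper training can administer the IMP". Adverse events are collected throughout.

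**The concern.** The stay falls on the first two infusions of remission-induction and the first two of rescue, and so observes the first E6011 doses of everyone except one group. Placebo is saline (section 9.4.1) and earlier E6011 use is an exclusion (criterion 27, section 9.3.2), so a placebo responder has had no E6011 before Week 12. The rule meanwhile repeats the stay for rescue entrants from the E6011 arm, who may already have had seven doses. A CDAI response to saline says nothing about how a patient will tolerate a first antibody infusion.

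What is at stake is whether a reaction in the hour after a first or second E6011 infusion is seen on site. Inference is not at stake: the affected infusions come after the Week 12 efficacy assessment.

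**Working it through.** The plan gives no figure of its own on this point, so the check starts from the dosing calendar.

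**Infusion weeks (section 9.4.1)**

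- Remission-induction: 0, 1, 2, 4, 6, 8, 10 (seven infusions)
- Rescue: 12, 13, 14, 16, 18, 20, 22
- Extension, Week 12 responders: 12, 16, 20, ..., 48

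**First two E6011 infusions, by route**

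| Route | Weeks | Period | Stay required |
|---|---|---|---|
| E6011 arm | 0, 1 | Remission-induction | 2 of 2 |
| Placebo, non-responder | 12, 13 | Rescue | 2 of 2 |
| Placebo, responder | 12, 16 | Extension | 0 of 2 |

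Nothing else in the schedule keeps these subjects on site. The post-infusion blood sample (within 10 minutes) is taken only from Week 0 to Week 10 (Table 4, footnote g). After Week 12 a responder's next visit is Week 16, whereas a rescue subject returns at Week 13.

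**How many subjects.** Section 9.7.2 gives 25 enrolled; at 1:1 that is 12 or 13 on placebo. The documents state no placebo CR70 rate, so 10% to 40% is an assumption.

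- Low: 12 × 0.10 = 1.2
- High: 13 × 0.40 = 5.2
- Chance of at least one affected subject, at the low end: 1 − 0.90^12 = 0.72

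These figures count use of the route, not harm.

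**How likely a reaction is.** For the 12-week dosing in Study 101 (28 patients), section 9.4.4 reports that "adverse events observed in 2 or more subjects included nasopharingitis in 5 subjects (17.9%), and headache, nausea, anal abscess" and Crohn's disease occurred in 2 patients each for the terms after the first. No hypersensitivity or infusion-reaction term appears. If that list is complete, any single unlisted term occurred in at most 1 of 28.

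- 1/28 = 3.6%; exact (Clopper-Pearson) two-sided 95% upper limit 18.3%
- Expected affected subjects with one given term at 3.6%: 1.2/28 = 0.04 to 5.2/28 = 0.19
- At the 18.3% limit: 1.2 × 0.183 = 0.22 to 5.2 × 0.183 = 0.95

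**Whether anyone is still to be dosed.** The protocol outline ends recruitment in October 2021. Allowing a full 42-day screening:

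- Last Week 12 infusion: 31-Oct-2021 + 42 + 84 days = 6-Mar-2022
- Last Week 16 infusion: 31-Oct-2021 + 42 + 112 days = 3-Apr-2022, or 10-Apr-2022 with the 7-day window
- Version 11.0 is dated 18-Apr-2022, which is 8 days later

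A screening period extended for isoniazid could push these dates back. The SAP synopsis runs recruitment to March 2022, but both documents end treatment in April 2022, leaving at most 30 − 18 = 12 days of dosing after version 11.0.

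**The case against.** The strongest reply is that the protocol never says what the stay is for. It falls on the first two doses of each intensive course (Weeks 0, 1, 2 and 12, 13, 14, then every two weeks), while the extension is four-weekly. A rule tied to dosing intensity fits the text and would also explain why pre-exposed rescue entrants must stay again. That reading is possible, but it would still leave drug-naive patients unobserved, and the visible text gives no reason for doing so.

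Second, the point may be moot. If responders complete dosing to Week 48 (336 days) by 30-Apr-2022, they started by 29-May-2021 and had their Week 16 infusion by 18-Sep-2021, seven months before version 11.0. The stated recruitment dates conflict with this unless late starters stop the extension early, so the documents do not settle the timing. This limits urgency.

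Third, the reaction figures are weak. The 3.6% is a ceiling for one term over 12 weeks and four dose levels. It is neither the rate for all hypersensitivity terms together nor the rate within an hour of infusion. That is correct, and the figures should be read only as showing that a large effect is not expected.

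Fourth, exclusion criterion 30 removes patients with a history of severe allergy, sites may have observed responders anyway, and the attachments and the handling manual, which are not shown, may contain the instruction. All of this reduces the weight of the point without closing the gap in the text.

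**Conclusion.** The omission is real and minor. In the visible text, one of the three routes to a first E6011 infusion carries no observation requirement, and the other two do. It concerns perhaps 1 to 5 subjects, on the assumed placebo CR70 rate and a near-equal split of 25. Section 9.4.4 reports no safety or tolerability issues up to 15 mg/kg, although 28 patients cannot exclude an uncommon reaction. An amendment made after version 11.0 would probably reach few or no infusions. The conclusion depends on no stay being specified in the attachments or manuals that are not shown.

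**What to change.** In section 9.4.1, extend the 60-minute stay to the first and second extension infusions (Weeks 12 and 16) of all Week 12 responders. It has to cover both arms: a rule for placebo responders alone would reveal allocation before the remission-induction database is locked.

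The change is one sentence and uses a procedure sites already carry out. The burden is at most two extra one-hour stays per responder, including E6011-arm responders who are not new to the drug. Because it concerns subject safety, section 11.1 requires regulatory notification and approval from every IRB/IEC involved. Amend this protocol only if a responder still has one of these infusions to come. If none does, carry the corrected rule into the next E6011 protocol with a similar crossover to active drug, and record in the clinical study report that no stay was required on this route.
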